13. History of having received (in the last 6 months) or currently receiving any systemic anti-neoplastic (including radiation) or immune-modulatory treatment (including systemic corticosteroids).
14. History of organ transplantation.
15. Any confirmed significant allergic reactions (urticaria or anaphylaxis) against any drug, or multiple drug allergies (non-active hay fever is acceptable).
16. Significant acute infection (e.g., influenza, local infection) or any other clinically significant illness within 2 weeks of randomization.
17. Clinically relevant ECG abnormalities on screening ECG including arrhythmias or marked QT abnormalities (QTcF < 300 msec or > 450 msec) at Screening.
18. Any of the following laboratory parameters at screening:
 - a) White blood cells (WBC) $< 3,000$ cells/ mm³
 - b) Neutrophil count < 1500 cells/mm³
 - c) Platelet count $< 140,000$ cells/mm³
 - d) aPTT > 40 seconds, INR > 1.2
 - e) Hemoglobin (Hgb) < 12 g/dL in females or < 13 g/dL in males.

19. Abnormal renal function including serum creatinine > ULN or calculated creatinine clearance < 70 mL/min (using the Cockcroft Gault formula).
20. Participation in an investigational drug or device study within 30 days prior to randomization.
21. Donation or loss of blood over 500 mL within 3 months prior to starting study medication.
22. Administration of any blood product within 3 months of randomization.
23. History or evidence of alcohol abuse (consumption of more than 2 standard drinks per day on average; 1 standard drink equals 10 grams of alcohol, for further guidance please see [Appendix 15](#)) and/or drug abuse within one year of randomization; positive test result for drugs of abuse at Screening.
24. Patients under judicial supervision, guardianship or curatorship.
25. Medical or social conditions that would potentially interfere with the patient's ability to comply with the study visit schedule or the study assessments.

4.2.3.3 Part 2c - CHB patients only:

1. *Women who are lactating.*
2. *History or other evidence of bleeding from esophageal varices.*
3. *Evidence of liver cirrhosis or decompensated liver disease such as ascites, esophageal or gastric varices, splenomegaly, nodular liver, jaundice, hepatic encephalopathy, portal hypertension.*
4. *One or more of the following laboratory abnormalities at screening:*
 - a) *Total serum bilirubin > ULN (exception Gilbert's disease).*
 - b) *INR > 1.1 ULN.*
 - c) *Serum albumin < 3.5 g/dL (< 35g/L).*

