17. *ECG at screening with clinically significant abnormalities, including QTcF interval (QT corrected using Fridericia's formula) ≥ 450 msec for males and ≥ 470 msec for females.*
18. *Abnormal renal function including serum creatinine $>$ ULN or calculated creatinine clearance < 70 mL/min (using the Cockcroft Gault formula).*
19. *Donation or loss of blood over 500 mL within 3 months prior to randomization.*
20. *Administration of any blood product within 3 months prior to randomization.*
21. *History of alcohol abuse (consumption of more than 2 standard drinks per day on average; 1 standard drink = 10 grams of alcohol) and/or drug abuse within one year of randomization; positive test result for drugs of abuse or alcohol breath test at screening.*
22. *Subjects under judicial supervision, guardianship, or curatorship.*

23. *Medical or social conditions that would potentially interfere with the subject's ability to comply with the study visit schedule or the study assessments.*

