4.6.1.5.1 Safety Laboratory Assessments

Laboratory safety tests shall be collected at time-points specified in the Schedule of Assessments (see [Appendix 1](#) to [Appendix 14](#)). Handling of residual samples is described in Section [4.6.1.5](#).

Additional blood or urine samples may be taken at the discretion of the Investigator if the results of any test fall outside the reference ranges, or clinical symptoms necessitate additional testing to monitor study subject safety. Where the clinical significance of abnormal lab results is considered uncertain, screening lab tests may be repeated before randomization to confirm eligibility. If there is an alternative explanation for a positive urine or blood test for drugs of abuse, e.g., previous occasional intake of a medication or food containing for example, codeine, benzodiazepines or opiates, the test could be repeated to confirm washout.

Additional blood and urine safety samples will also be collected at the time of a serious adverse event.

In the event of unexplained abnormal clinically significant laboratory test values, the tests should be repeated immediately and followed up until they have returned to the normal range and/or an adequate explanation of the abnormality is found. Results of clinical laboratory testing will be recorded on the eCRF or be received as electronically produced laboratory reports submitted directly from the central laboratory.

The following blood and urine samples will be collected:

- Hematology: leucocytes, erythrocytes, hemoglobin, hematocrit, platelets, differential count (neutrophils, eosinophils, basophils, monocytes, lymphocytes), mean corpuscular hemoglobin (MCH) and mean corpuscular hemoglobin concentration (MCHC).
- Blood chemistry: ALT, AST, total and indirect bilirubin, ALP, blood urea nitrogen (BUN), gamma-glutamyl transferase (GGT) (at Screening only), *glutamate dehydrogenase (GLDH)*, creatine phosphokinase (at Screening only), total protein, albumin, creatinine *and calculated creatinine clearance (using the Cockcroft Gault formula)*, glomerular filtration rate (GFR) calculated (*MDRD4 method*), uric acid, cystatin c, fasting glucose, total cholesterol, LDL cholesterol, HDL cholesterol, triglycerides, sodium, chloride, potassium, calcium, magnesium, phosphate and bicarbonate.
- Coagulation: prothrombin time (PT), International Normalized Ratio (INR), activated partial thromboplastin time (aPTT)

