4.7.1.1 Discontinuation from Study Drug

Study subjects must discontinue study drug if they experience any of the following:

- Pregnancy
- A serious adverse event (SAE) considered by the Investigator to be related to treatment with RO7062931.

Study subjects who discontinue study drug prematurely will be asked to return to the clinic for a study completion/early termination visit and may undergo follow-up assessments. The primary reason for premature study drug discontinuation should be documented on the appropriate eCRF.

Study subjects who discontinue study drug prematurely for safety reasons will not be replaced. Study subjects who discontinue study drug prematurely for non-safety reasons may be replaced. The Sponsor should be informed of subjects' discontinuations from the study or from the study drug.

Part 2: CHB Patients

Individual patients must discontinue RO7062931/placebo if they experience any of the following:

- Safety and tolerability issues, e.g., acute reactions, not tolerable and not manageable with symptomatic treatment.
- Grade 4 ALT (i.e., $\geq 10 \times \text{ULN}$) as defined by the Division of Acquired Immunodeficiency Syndrome (AIDS) Table for Grading the Severity of Adult and Pediatric Adverse Events ([DAIDS AE grading table](#)) confirmed within 48-72 hours (*not for Part 2c*).
- Grade 3 ALT (i.e., $> 5x$ to $< 10 \times \text{ULN}$) combined with total bilirubin $> 2 \times \text{ULN}$ (of which $> 35\%$ is direct bilirubin), or Grade 3 ALT and INR > 1.5 .
- Any other confirmed (within 48-72h) Grade 4 laboratory abnormality deemed clinically significant (based on Investigator's assessment).
- Development of liver decompensation (ascites, varices, Child-Pugh Class B or C clinical classification).
- *Grade 3 renal* adverse events defined as creatinine $\geq 50\%$ from baseline *and/or* *eGFR* $< 60 \text{ ml/min/1.73 m}^2$.
- Development of resistance in a CHB patient is suspected if the patient experiences an increase in serum HBV DNA of $> 1 \log_{10}$ (10-fold) over nadir during the treatment period, i.e., virological breakthrough.
- NUC analogue discontinuation due to safety issues or resistance development.

All prematurely discontinued patients will have assessments performed at the end of treatment with RO7062931/placebo listed in the SoAs tables. If a patient discontinues study drug between study visits, he/she should be called for an unscheduled visit to have these assessments performed.

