5.1.3 Non-Serious Adverse Events of Special Interest (Immediately Reportable to the Sponsor)

Non-serious adverse events of special interest are required to be reported by the Investigator to the Sponsor immediately (i.e., no more than 24 hours after learning of the event; see Section 5.4.2 for reporting instructions). Adverse events of special interest for this study include the following:

- *Cases of an isolated elevated ALT or AST ≥ 10 ULN (Section 5.2 and 5.3.5.6).*
- *Cases of an elevated ALT or AST in combination with either an elevated bilirubin or clinical jaundice, as defined in Section 5.3.5.6.*
- *Suspected transmission of an infectious agent by the study drug, as defined below:
Any organism, virus, or infectious particle (e.g., prion protein transmitting transmissible spongiform encephalopathy), pathogenic or non-pathogenic, is considered an infectious agent. A transmission of an infectious agent may be suspected from clinical symptoms or laboratory findings that indicate an infection in a patient exposed to a medicinal product. This term applies only when a contamination of the study drug is suspected.*
- *Severe injection site reactions*
- *Grade 3 renal adverse events defined as creatinine $\geq 50\%$ from baseline *and/or* eGFR < 60 mL/min/1.73 m².*

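### The renal stop rule and AESI use an absolute eGFR limit with no named equation and no baseline reference, while entry is judged by creatinine and Cockcroft-Gault clearance, so the sections need reconciling

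*Combined protocol and SAP*

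**What the plan says.** **Entry.** Exclusion 19 in Section 4.2.3.2 (Parts 2a/2b) and exclusion 18 in Section 4.2.3.3 (Part 2c) share the same wording: "Abnormal renal function including serum creatinine > ULN or calculated creatinine clearance < 70 mL/min (using the Cockcroft Gault formula"). No entry criterion names an eGFR limit.

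**Laboratory.** Section 4.6.1.5.1 lists two renal estimates under blood chemistry: a Cockcroft-Gault creatinine clearance and "glomerular filtration rate (GFR) calculated" by MDRD4. Neither the MDRD4 constant nor the creatinine ULN is given.

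**Mandatory stop.** Section 4.7.1.1, for Part 2: "Individual patients must discontinue RO7062931/placebo if they experience any of the following". The list includes Grade 3 renal "adverse events defined as creatinine" at least 50% from baseline and/or eGFR below 60 mL/min/1.73 m². Only the creatinine limb mentions baseline. In the same list, Grade 4 ALT (outside Part 2c) and other Grade 4 laboratory values must be confirmed within 48 to 72 hours; the renal item has no confirmation step.

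**AESI.** Section 5.1.3 repeats the definition, with "eGFR < 60 mL/min/1.73 m²" as a sufficient limb, and requires reporting within 24 hours.

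**Related rules.** Section 5.3.5.8 records a pre-existing condition as an adverse event only if it worsens. Inclusion 9 of Section 4.2.2.2 and inclusion 7 of Section 4.2.2.3 ask for normal screening chemistry, except where another criterion applies or the investigator and Medical Monitor judge the value not clinically significant.

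**The concern.** Entry and stopping are measured on different scales. Cockcroft-Gault depends on body weight and is in mL/min. MDRD4 does not use weight and is per 1.73 m². A heavier, older patient can therefore pass "calculated creatinine clearance < 70 mL/min (using the Cockcroft Gault formula") as an exclusion test and yet sit below 60 on MDRD4. Because the eGFR limb is absolute and joined by and/or, no change is needed to meet it.

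Two things are at stake. A patient with unchanged renal function could be taken off RO7062931 under a mandatory rule. The same patient would be counted as a Grade 3 renal AESI in a study whose primary objective is safety. Part 2c cohorts start with about 8 patients, so one such case is 1/8 = 12.5% of a cohort, and Section 4.7.1.1 does not replace patients who discontinue for safety reasons.

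**Working it through.** The plan states no figure to reproduce; the check is whether both conditions can hold in one eligible patient.

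**Inputs from the documents:** age 18 to 65, BMI 18 to 32 kg/m², creatinine not above ULN, Cockcroft-Gault (CG) at least 70 mL/min, eGFR limit 60 mL/min/1.73 m², MDRD4 as the GFR method.

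**Assumptions:** the formula coefficients (MDRD4 constant k taken as 175 or 186) and the creatinine ULN, which is varied.

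- CG = (140 − age) × weight / (72 × SCr), × 0.85 if female
- MDRD4 = k × SCr^−1.154 × age^−0.203, × 0.742 if female

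**Step 1: two example patients.**

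| Patient | CG | MDRD4, k = 175 | MDRD4, k = 186 |
|---|---|---|---|
| Woman, 60 y, 75 kg, 1.0 mg/dL | 80 × 75 / 72 × 0.85 = 70.8 | 56.6 | 60.1 |
| Man, 62 y, 90 kg, 1.25 mg/dL | 78 × 90 / (72 × 1.25) = 78.0 | 58.5 | 62.2 |

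Both satisfy the clearance criterion. Both meet the stop rule with k = 175 and neither does with k = 186. Each also needs a ULN at or above the creatinine shown.

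**Step 2: creatinine at which MDRD4 equals 60, age 65.** SCr = (k × 65^−0.203 [× 0.742] / 60)^(1/1.154).

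| | k = 175 | k = 186 |
|---|---|---|
| Men | 1.213 mg/dL | 1.279 mg/dL |
| Women | 0.937 mg/dL | 0.988 mg/dL |

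At the k = 175 values, CG reaches 70 from 70 × 72 × 1.213 / 75 = 81.5 kg (men) and 70 × 72 × 0.937 / (75 × 0.85) = 74.1 kg (women). At 1.70 m these are BMI 28.2 and 25.6, inside the permitted range.

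**Step 3: overlap at screening over a range of ULN** (height fixed at 1.75 m for men and 1.62 m for women, full BMI range).

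| | k = 175 | k = 186 |
|---|---|---|
| Men | none at ULN 1.20 or below; from age 55 at 1.25, 44 at 1.30, 36 at 1.35 | none at 1.25 or below; from age 60 at 1.30, 48 at 1.35 |
| Women | none at 0.90 or below; from age 61 at 0.95, 45 at 1.00, 27 at 1.10 | none at 0.95 or below; from age 61 at 1.00, 36 at 1.10 |

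Women must be of non-childbearing potential, so the older ages matter most in that row.

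**Step 4: if the ULN closes the overlap.** Take a 65-year-old whose creatinine sits at an assumed ULN of 1.20 (man) or 0.90 mg/dL (woman). The rise needed to reach eGFR 60 is:

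- Man: 1.213 / 1.20 − 1 = about 1% (k = 175); 1.279 / 1.20 − 1 = about 7% (k = 186)
- Woman: 0.937 / 0.90 − 1 = about 4% (k = 175); 0.988 / 0.90 − 1 = about 10% (k = 186)

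The creatinine limb of the same definition asks for 50%.

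**The case against.** **Missing figures.** The screening overlap depends on a ULN and a constant that the documents do not state. This stands, and the claim is conditional for that reason.

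**Screening gates.** MDRD4 GFR is listed under chemistry, so the normal-range inclusion criterion could catch a low value, and exclusion 18/19 is worded as a non-exhaustive list. This narrows the gap. It does not close it, because the inclusion criterion exempts values covered by other criteria and values judged not clinically significant.

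**No adverse event without worsening.** The stop rule concerns adverse events, and under Section 5.3.5.8 an unchanged low value would not be one. That is a reasonable reading, but it conflicts with the literal definitions in Sections 4.7.1.1 and 5.1.3. Section 5.3.5.4 does not settle it: it makes a laboratory value an adverse event if it leads to a treatment change, which is the question at issue.

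**A deliberate floor.** An absolute safety limit in a first-in-human study is a legitimate choice. Agreed; the point is that the text does not say how it applies to a patient already below it.

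**Stronger readings the documents do not support.** A reader might infer that a patient would meet the rule on Day 1. Only Appendix 11 schedules Day 1 chemistry; Appendix 13 has Day −7 to −4 and then Week 2, and Parts 2a/2b have Day −1 and Day 2. A reader might also infer that stopping makes the patient an efficacy failure. Section 6.6.3 imputes non-response only for missing HBsAg from 24 weeks after treatment, and discontinued patients continue follow-up. Finally, the creatinine limb gives no direction of change; that is a minor wording point.

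**Conclusion.** The mismatch is in the current text: different equation, different units, and an eGFR limb that is sufficient alone with no baseline reference in both the stop rule and the AESI. MDRD4 is the natural reading of eGFR, because Section 4.6.1.5.1 names it, but neither definition says so.

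Read literally, an eligible patient with stable kidneys can meet both definitions if the laboratory ULN exceeds about 1.21 mg/dL (men) or 0.94 (women) at age 65 with k = 175, or about 1.28 and 0.99 with k = 186. At lower ULNs this does not arise at screening, but the two limbs remain far apart: a creatinine rise of about 1% to 10% against 50% in the cases shown. The documents do not allow an estimate of how many patients would be affected. The point merits correction because the rule is mandatory, the cohorts are small and the repair is cheap.

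**What to change.** Reconcile Sections 4.2.3.2, 4.2.3.3, 4.6.1.5.1, 4.7.1.1, 5.1.3 and 5.3.5.8 so that they state:

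1. which equation, with its constant, defines eGFR in the stop rule and the AESI;
2. how a value already below the limit at baseline is handled in each;
3. how the AESI definition fits with the rule that a pre-existing condition is an adverse event only if it worsens.

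The direction of the creatinine change can be stated in the same edit. The clinical rule and the threshold are for the sponsor to decide.

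The cost is wording. Both renal estimates are already in the blood chemistry panel, so no new sample or visit is needed.

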Blood samples will be collected at baseline (BL; Day 1 pre-dose) and throughout the study, as detailed in the SoA, to monitor for the development of drug resistance. Sequencing of the complete HBV genome will be performed for all viral resistance monitoring samples at BL if viral load is ≥ 1000 copies/mL. For patients whose BL sample contains < 1000 copies/mL and therefore, a BL sequence cannot be established, an archived sample should be provided with a reasonable effort if available in order to get a BL sequence. If a patient experiences an increase in serum HBV DNA level of more than $1\log_{10}$ (10-fold) over nadir (viral breakthrough) during the treatment period or follow-up period of the study, an ad hoc (unscheduled) blood sample will be taken to confirm the breakthrough. Samples from confirmed viral breakthrough and subsequent follow-up visits will be sent for population sequencing. Other sequencing analyses (e.g., ultra deep sequencing) and phenotypic analysis may be performed in addition.

Virological breakthrough should be reported as an adverse event.

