If ALT elevations are associated with increased HBV DNA levels, virological breakthrough will be suspected (see Section 4.6.1.5.4).

ALT elevations during follow-up

- *Isolated ALT elevation with preserved hepatic function:*
 - *ALT 5 to 10 x ULN: Repeat LFTs every week.*
 - *ALT >10 x ULN: Repeat LFTs twice weekly until ALT level <5 x ULN.*
- *ALT elevation accompanied by declining liver synthetic and excretory functions:*
 - *ALT 5 to 10 x ULN: Repeat LFTs and ALT/AST every week.*
 - *ALT >10 x ULN: Repeat LFTs and ALT/AST twice weekly until ALT level < 5 x ULN.*
 - *Investigate the CHB patient for potential etiologies of the laboratory changes.*
 - *If alternative reasons/diagnoses cannot explain the laboratory changes, a potentially delayed DILI will be suspected and CHB patient will be monitored accordingly.*

In participants who have not discontinued NUC therapy if ALT elevations are associated with increased HBV DNA levels, virological breakthrough will be suspected (see Section 4.6.1.5.4).

The Investigator should aim to exclude development of decompensated liver disease. Patients who develop signs of decompensated liver disease (e.g., ascites, variceal hemorrhage, Child-Pugh Class B or C clinical classification [[Appendix 16](#)]) should discontinue study treatment (Section 4.7.1.1). Patients who develop flares should be monitored more closely with additional unscheduled visits and laboratory assessments.

At the discretion of the Investigator, study treatment can be discontinued.

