6.6.1 Viral Dynamic Response Analyses

Summary descriptive statistics will be used to summarize the viral dynamic response outcome measure of quantitative HBsAg (log₁₀), actual and change from baseline in quantitative HBsAg at each time-point by dose group. Rate of decrease in quantitative HBsAg will also be summarized using descriptive statistics.

Plots of quantitative HBsAg (actual and change from baseline) over time will be utilized to compare the longitudinal profiles across doses.

Mean (SD) of HBsAg (actual and change) will be calculated for each dose level and plotted on one plot, different line types and symbols used to differentiate the dose levels. In addition, individual patient data will be plotted over time, one plot for each dose level.

Further exploration may include plots of quantitative HBsAg over time, grouped by baseline characteristics and/or demographics of interest.

All other exploratory viral dynamic responses will be listed by time-points as a minimum.

Further exploration of these exploratory responses for potential treatment effects may include longitudinal graphs and/or summaries.

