HBsAg, HBeAg Qualitative; HBsAg/Anti-HBs Complex; Anti Hbe; AntiHBs		X	X ^b		X ^b	X ^b	X ^b		X ^b	X ^b					X ^b	
Viral Genotypes			X ^b													
HBV DNA, Viral Resistance sequencing		X	X ^b		X ^b	X ^b	X ^b		X ^b	X ^b					X ^b	
HBV RNA, HBcrAg			X ^b		X ^b	X ^b	X ^b		X ^b	X ^b					X ^b	
Clinical Genotyping			X ^l													
Ambulatory Visit	X	X	X	X	X	X	X	X	X	X	X	X	X	X	X	X
Randomisation			X													
Adverse Events	X	X	X	X	X	X	X	X	X	X	X	X	X	X	X	X

Appendix 13
Schedule of Assessments – Part 2c, QW Doses for 48 Weeks, Main Table (cont.)

Period	Discontinuation ^e	Follow Up Visit	Follow Up Visit	Follow Up Visit	Follow Up Visit	Follow Up Visit	Follow Up Visit	Follow Up Visit	Follow Up Visit	Follow Up Visit ^h
Day		week 50	week 52	week 54	week 56	week 58	week 60	week 64	week 68	week 72
		+/-3	+/-3	+/-3	+/-3	+/-3	+/-7	+/-7	+/-7	+/-7
Assessments										
FSH ^g										
Substance Use										
Medications ^c										
PK Blood Sample ^q	X	X	X	X						
Urine PK Sample ^r										
NUC PK ^s										
HBsAg Quantitative	X	X	X	X	X	X	X	X	X	X
HBsAg, HBeAg Qualitative; HBsAg/Anti-HBs Complex; Anti Hbe; AntiHBs	X		X		X	X	X	X	X	X
Viral Genotypes										
HBV DNA, Viral Resistance sequencing	X		X		X	X				X
HBV RNA, HBcrAg	X		X		X	X				X
Clinical Genotyping										
Ambulatory Visit	X	X	X	X	X	X	X	X	X	X
Randomisation										
Adverse Events	X	X	X	X	X	X	X	X	X	X
Previous and Concomitant Treatments	X	X	X	X	X	X	X	X	X	X

Appendix 13

Schedule of Assessments – Part 2c, QW Doses for 48 Weeks, Main Table (cont.)

- a) For those patients who do not have a liver biopsy, Fibroscan® or equivalent test within the past 6 months from Screening.
- b) Pre -dose.
- c) Daily administration of NUC and weekly clinic SC administration of RO7062931 or RO7062931 and PEG-IFN
- d) Blood sample for RO7062931 PK and safety laboratory assessment will also be collected in the event of an SAE.
- e) Discontinuation visit: in case of early termination, a patient should be called for this visit and assessments should be performed as listed.
- f) Blood beta -human chorionic gonadotropin (β -HCG) for pregnancy test at screening, other occasions, at any time a secondary amenorrhea of more than 1 week occurs.
- g) FSH only for females and to confirm post -menopausal status.
- h) If necessary, the patients may be asked to return for additional follow-up visits.
- i) Body weight will be measured at each visit for dosing

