- j) Baseline sample will be assessed and in case of an immune driven AE/AE suggestive of immunological involvement occurs, an unscheduled sample will be collected and analyzed along with follow-up time-points.
- k) Complete physical examination, is required at screening. At all other visits (or as clinically indicated), limited, symptom-directed physical examinations should be performed at the discretion of the Investigator.
- l) One single whole blood sample to be collected for genetic analysis at any time after randomization. If the sample is not collected at the scheduled time -point, it can be collected at any other time -point. Only one sample will be collected per patient.
- m) In case an autoimmune driven AE/AE suggestive of autoimmunological involvement occurs, an unscheduled sample will be collected and analyzed.
- n) HAV, HCV, HDV, HEV, and HIV.
- o) ANA, AMA, ASMA, a-TPO, anti-thyroglobulin, anti-platelet.
- 
- q) Serial PK samples will be taken at pre-dose and 0.5, 1, 2, 4, 6 and 8 hours post-dose on Day 1 of Weeks 1, 12, 24, and 48.
A Day 2 PK sample (24 hour time point) will be collected in Weeks 1, 12, 24, and 48.
A pre-dose sample will be collected in Weeks 2, 13, and 25 representing 168 hours post the previous dose in Weeks 1, 12, and 24, respectively. An additional sample will be collected in Week 49 at 168 hours post the 48 week dose.
Sparse PK sampling at pre-dose and within a range of 2-4 hours post-dose will be made on Day 1 of Weeks 4, 8, 18, 30, and 36.
One PK sample is required on the follow up visits in Weeks 50, 52, and 54, and one PK sample is required upon discontinuation.

Appendix 13
Schedule of Assessments – Part 2c, QW Doses for 48 Weeks, Main Table (cont.)

- r) All voided urine will be collected in two pools from 0-4 hours and 4-8 hours post-dose on Day 1 of Weeks 1, 12, 24, and 48.
- s) PK samples for NUC analysis on Day 1 of Week 1 pre-NUC dose and 2-4 hours post-NUC dose. One sample collected if DNA rebound is detected.

█ [REDACTED]

█ [REDACTED]

- * Keep all left over sample for patients participating in the RBR program.

Appendix 14

Schedule of Assessments - Part 2c, QW Doses for 48 Weeks, Detailed Table

Period	Week	Day	Scheduled Time (h)	PK Blood Sample ^a	Urine PK Sample ^b	NUC PK Sample ^c	
Screening		-7 to -4					
Treatment Period	1	1	Predose	x		x	
			0.5	x			
			1	x	x		
			2	x			
			4	x		x	
			6	x			
			8	x	x		
	24	x					
	2	7		Predose	x		
	4	1		Predose	x		
			2	x			
			4				
	8	1		Predose	x		
			2	x			

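### On the 48-week schedule HBV DNA is not tested between Week 24 and Week 48, so the mandatory virological-breakthrough stop has no scheduled data to act on until the last dosing visit.

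*Combined protocol and SAP*

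**What the plan says.** Section 4.7.1.1 introduces its Part 2 list with "Individual patients must discontinue RO7062931/placebo if they experience any of the following". The list includes virological breakthrough: "Development of resistance in a CHB patient is suspected if the patient experiences an increase in serum HBV DNA of" more than 1 log10 (10-fold) over nadir during treatment. The Grade 4 ALT criterion in the same list is marked as not applying to Part 2c. The breakthrough criterion carries no such exemption, so it binds Cohort 10 for up to 48 weeks of weekly dosing (section 4.4.2.1).

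Section 4.6.1.5.4 leaves the timing of resistance monitoring to the Schedule of Assessments. It adds that once a rise has been seen, "an ad hoc (unscheduled) blood sample will be taken to confirm the breakthrough". It also requires virological breakthrough to be reported as an adverse event.

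In Appendix 13 the row labelled "HBV DNA, Viral Resistance sequencing" is marked at Day -7 to -4, Day 1 and Weeks 4, 8, 12, 18, 24 and 48. It is blank at Weeks 25, 30, 36 and 42. Footnote q shows that Week 48 is the last dose: "An additional sample will be collected in Week 49 at 168 hours post the 48 week dose".

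Two other provisions could lead to an HBV DNA test. Section 4.6.1.5.1 states "Additional blood or urine samples may be taken at the discretion of the Investigator" when a result is out of range or symptoms call for it. Section 5.2.1.2 states "If ALT elevations are associated with increased HBV DNA levels, virological breakthrough will be suspected".

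**The concern.** A mandatory stopping rule works only if the measurement behind it is taken often enough. For Weeks 25 to 47 of the 48-week schedule, no HBV DNA measurement is planned.

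- **Patient management.** A persistent breakthrough after Week 24, without raised ALT or symptoms, would be found at Week 48. By then the patient would have received the doses that section 4.7.1.1 says should have been withheld.
- **Reporting.** A transient breakthrough that resolves before Week 48 could go unseen. It would then be missing from the adverse event reports and from the HBV DNA listing, for which section 6.6.1 promises only that "All other exploratory viral dynamic responses will be listed by time-points as a minimum". Section 3.3.3 names maintenance of HBV DNA below the LLOQ as an exploratory outcome for Part 2c, and it has no scheduled data in this period.
- **Linked check.** Under Appendix 13 footnote s, NUC concentrations are sampled after Week 1 only when DNA rebound is detected. Without an HBV DNA test, that adherence check also stays dormant.

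The point concerns Cohort 10 and any optional cohort (11 or 12) placed on this schedule. Cohorts 11 and 12 may enrol treatment-naïve, viraemic patients.

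**Working it through.** The plan states no figure for this gap, so there is none to reproduce.

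**1. Schedule marks (Appendix 13, treatment period)**

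| Row | Wk 24 | Wk 25 | Wk 30 | Wk 36 | Wk 42 | Wk 48 |
|---|---|---|---|---|---|---|
| HBV DNA / resistance | X | – | – | – | – | X |
| HBV RNA, HBcrAg | X | – | – | – | – | X |
| Quantitative HBsAg | X | X | X | X | X | X |
| Blood chemistry | X | – | X | X | X | X |
| ADA | X | – | X | X | X | X |

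The HBV DNA row has 16 cells against 16 column headings. Neighbouring rows carry marks in the columns where it is blank, so the visits exist and blood is drawn at them.

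**2. Intervals between on-treatment tests**

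Tests fall at Weeks 1, 4, 8, 12, 18, 24 and 48. Successive differences are 3, 4, 4, 6, 6 and 24 weeks. With the ±7-day windows at both ends, the last gap is 24 ± 2, or 22 to 26 weeks. Weeks 25 to 47 contain 23 weekly doses.

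**3. Detection delay**

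Assume a persistent breakthrough, onset uniform over Weeks 24-48, and no unscheduled test. For a testing interval of length L, mean delay = L/2 and maximum = L.

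- Current schedule: L = 24, mean 12 weeks, maximum 24.
- Tests added at Weeks 30, 36 and 42: L = 6, mean 3 weeks, maximum 6.

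**4. Doses averted**

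Assume pre-dose samples, with the result available before the next weekly dose. Doses averted = 48 − week of detection.

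- Current: 48 − 48 = 0. It would be 1 only if the Week 48 result came back the same day.
- With the added tests: detection at Week 30, 36, 42 or 48 averts 18, 12, 6 or 0 doses. Mean = (18 + 12 + 6 + 0)/4 = 9.
- If confirmation adds one week: 17, 11, 5 and 0, mean 33/4 = 8.25.

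**5. Chance of at least one event**

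The documents give no breakthrough rate. The per-patient risks p over Weeks 24-48 below are assumptions. Formula: 1 − (1 − p)^n.

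| n | p = 1% | p = 5% | p = 10% |
|---|---|---|---|
| 8 | 8% | 34% | 57% |
| 22 | 20% | 68% | 90% |
| 30 | 26% | 79% | 96% |

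Section 6.1 can be read as allowing expansion to 30 per cohort. Section 4.3 can be read as 30 across Cohorts 9 and 10 together, which leaves at most 30 − 8 = 22 for Cohort 10.

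**The case against.** The strongest reply is that the lighter testing is deliberate and reasonable. Cohort 10 patients have had at least 12 months on a NUC (entecavir or a tenofovir) and HBV DNA below the LLOQ at screening and in the preceding 6 months, and they continue the NUC. Breakthrough may be rare. Nothing in the documents shows that further RO7062931 worsens a breakthrough, and section 1.2.1 reports in vitro activity against NUC-resistant virus. This supports treating the point as moderate. It does not explain a mandatory stop without data, and the visible text gives no reason for the change from 6-week to 24-week spacing.

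The plan also has several safeguards:

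- PD sampling times may be changed as data emerge (4.6.1.5.4), and an interim analysis falls at Week 24 for the first 8 patients (6.11).
- Residual blood may be used for exploratory HBV assays (4.6.1.5).
- ALT above 5 × ULN calls for a search for causes (5.2.1.2), and chemistry is run at Weeks 30, 36 and 42.
- HBV DNA is tested again at Weeks 52, 56, 58 and 72, so a persistent event would eventually be found.

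All of these are optional, depend on another signal, or come too late to stop dosing. The liver tests listed for ALT monitoring do not include HBV DNA. The ad hoc sample only confirms a rise already seen.

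Appendix 13 also has internal oddities. For example, urine PK is marked at Week 36, which footnote r does not list. The row is therefore worth checking against the source table. If its last mark belonged one column later, at Week 49, the gap would be 25 weeks and the point would stand. Two other viral rows show the same blanks.

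Finally, the event probabilities rest on assumed risks and span 8% to 96%, so they should carry little weight.

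**Conclusion.** The concern holds. On the 48-week schedule the breakthrough stop applies throughout treatment, but from Week 24 its first scheduled measurement comes 24 weeks later, at the final dosing visit. The longest earlier interval is 6 weeks. The 24-week gap is read directly from the schedule. The 12-week mean delay and the absence of averted doses depend on persistent onset spread evenly over Weeks 24-48, no unscheduled test, and results returned within a week. How often this would matter is unknown, because no breakthrough rate is given.

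This should be corrected, but it does not undermine the trial's main results. Confidence is medium, given the modest expected risk in suppressed patients, the discretionary safeguards and the inconsistencies elsewhere in the table.

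**What to change.** Mark HBV DNA in Appendix 13 at Weeks 30, 36 and 42. The longest on-treatment interval returns to 6 weeks, the spacing already used from Week 12 to Week 24. The same change gives the rebound-triggered NUC sample something to respond to. Any optional cohort on the 48-week schedule should follow the amended table.

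The cost is three extra assays per patient: 3 × 8 = 24 for the initial cohort, or 3 × 30 = 90 if a cohort reaches 30. No new visit or blood-draw occasion is needed, only an amendment to the schedule table.
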